10.2 Adverse Events

Adverse events (AEs) will be summarized and presented using primary MedDRA System Organ Classes (SOCs) and preferred terms (PTs) according to the version of the MedDRA coding dictionary used for the study at the time of database lock. The actual version of the MedDRA coding dictionary used will be noted in the AE tables and in the clinical study report. Specific adverse events will be counted once for each subject for calculating percentages, unless stated otherwise. In addition, if the same adverse event occurs multiple times within a subject, the highest severity and level of relationship to investigational product will be reported.

[figure not shown]
10.2.1 Treatment-Emergent Adverse Events

Unless noted otherwise, all summaries included treatment-emergent AEs (TEAEs) only. TEAEs are defined as any event that begins or worsens in severity after initiation of study drug through 30 days post-study drug dosing. Events where the onset date is the same as the study treatment start date are assumed to be treatment-emergent. All treatment-emergent AEs will be summarized overall, as well as by primary MedDRA SOC and Preferred Term. The SOCs will be presented in alphabetical order, and the PTs will be presented in alphabetical order within each SOC.

The number and percentage of subjects experiencing treatment-emergent AEs will be summarized.

10.2.2 Adverse Event Overview

[figure not shown]
An overview of AEs will be presented consisting of the number and percentage of subjects experiencing at least one event for each of the following AE categories. Treatment differences between each upadacitinib dose group versus the placebo group together with 95% CI for each AE category below will also be provided on SS1 for Period 1.

- Any treatment-emergent AE
- Any treatment-emergent AE related to upadacitinib (or matching placebo) according to the investigator
- Any treatment-emergent AE related to prednisone/prednisolone (or matching placebo) according to the investigator
- Any treatment-emergent AE with CTCAE grade ≥ 3
- Any serious treatment-emergent AE
- Any treatment-emergent AE leading to discontinuation of study treatment (upadacitinib or matching placebo)
- Any treatment-emergent AE leading to death
- Any treatment-emergent AE related to COVID-19
- Any treatment-emergent AEs of Special Interest (AESIs)
- Any treatment-emergent AEs of bone fracture and retinal detachment
- All deaths
 - \circ Deaths occurring ≤ 30 days after last dose of study treatment
 - Deaths occurring > 30 days after last dose of study treatment
 - COVID-19 related deaths

10.2.3 Treatment-Emergent Adverse Events by SOC and/or PT

Treatment-emergent adverse events will be summarized by SOC and PT; by maximum relationship to upadacitinib (or matching placebo) as assessed by the investigator (e.g., reasonable possibility or no reasonable possibility) and SOC and PT; by maximum relationship to prednisone/prednisolone (or matching placebo) and SOC and PT, by maximum toxicity and SOC and PT; and by subject number and SOC and PT. Specific adverse events will be counted once for each subject for calculating percentages, unless stated otherwise. In addition, if the same adverse event occurs multiple times within a subject, the highest severity and level of relationship to investigational product will be reported.

In addition, treatment-emergent adverse events will be summarized by PT and sorted by decreasing frequency for the total active group.

10.2.4 Treatment-Emergent Adverse Events per Patient-Years of Exposure

Exposure-adjusted TEAEs per 100 patient-years will be provided, where TEAEs per 100 patient-years of exposure are defined as the number of TEAEs divided by the total exposure in 100 patient-years. The study drug exposure is defined as the last dose date minus the first dose date plus 30 days. Exposure-adjusted TEAEs will be summarized on SS1 for Period 1 and SS LT for long-term. Treatment differences between each upadacitinib dose group versus the placebo group together with 95% CI may also be provided on SS1 for Period 1 and SS LT for the long-term.

The exposure-adjusted incidence rate (EAIR) (censored at the time of first event) may be conducted for selected AESI endpoints as appropriate on SS LT for long-term.

10.2.5 Deaths, Serious Adverse Events, and Adverse Events Leading to Study Treatment Discontinuation

Treatment-emergent serious adverse events (SAEs), TEAEs leading to premature discontinuation of study treatment, and TEAEs leading to death will be summarized by SOC and PT.

Tabular listings will be provided for all deaths, all SAEs, Treatment Emergent SAEs, TEAEs leading to death, TEAEs leading to premature discontinuation of study treatment.

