By preferentially targeting JAK1, it is anticipated that upadacitinib will demonstrate the ability to abrogate signaling of key cytokines involved in the pathogenesis of GCA. Extensive preclinical, ex vivo, and in vivo studies have demonstrated robust inhibition of the JAK1-dependent cytokines IL-6 and Interferon gamma (IFN-γ). These two cytokines have been strongly implicated in the pathogenesis of GCA. IL-6 receptor blockade with tocilizumab has demonstrated efficacy in GCA in Phase 2 and Phase 3 studies. ^{4,5} However, preclinical and translational human studies have suggested that even in the setting of high dose CS with resultant reduction of IL-6 pathway, there persists a level of subclinical inflammation driven largely by IFN-γ. ^{11,12} Serial biopsies of patients with GCA treated with high dose CS have demonstrated that the IL-6 cytokine pathway is highly responsive to standard CS therapy, whereas the IFN-γ pathway is resistant to steroid-mediated immunosuppression. ¹³ Moreover, direct IFN-γ blockade abrogates STAT1 activation, reduced expression of ICAM-1, CXCL9, 10, 11 and prevents macrophage adhesion/infiltration.

Similarly, treatment with the relatively non-selective JAK inhibitor to facitinib in a translational model of human GCA¹⁴ demonstrated abrogation of STAT-1 signaling, reduced blood levels of IFN-γ, and prevention of T cell and macrophage accumulation in the vessel wall.

Clinically, the persistence of smoldering inflammation is supported by studies in which patients with GCA, or the closely related large vessel vasculitis Takayasu's arteritis, who were treated with the IL-6 pathway blocker tocilizumab, demonstrated persistent vasculitis of medium-sized and large vessels on autopsy despite apparent clinical response to therapy. ^{15,16} These data suggest that although IL-6 receptor blockade can provide reduction in flares when used continuously on the background of a forced CS taper, ultimately targeting the CS/IL-6 resistant Th1 responses will be necessary to resolve chronic smoldering vasculitis. Among those with a good response to tocilizumab in a 1-year study, over half of subjects relapsed (as early as 3 months) after discontinuation of IL-6R blockade. ¹⁷

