Subjects assigned to either dose of upadacitinib who achieve sustained remission for at least 24 consecutive weeks prior to the Week 52 Visit (at the end of Period 1) will be rerandomized in a 2:1 ratio to either continue on upadacitinib or switch to placebo in Period 2. Re-randomization will be stratified by Baseline disease status (new onset disease, relapsing disease). Subjects who achieved sustained remission for at least 24 consecutive weeks prior to the Week 52 visit (at the end of Period 1) who were assigned to placebo in Period 1 will continue to receive placebo in Period 2.

At Week 52, subjects who have absence of GCA signs and symptoms AND are CS-free, but do not achieve sustained remission for at least 24 consecutive weeks prior to the Week 52 Visit will continue in Period 2 on their originally randomized treatment assignment. All other subjects will be discontinued from study drug and the study at the end of Period 1.

In Period 2, subjects who experience a flare will start open-label CS escape therapy with prednisone or prednisolone at investigator's discretion. Subjects meeting flare criteria will return within approximately 4 weeks after the visit in which flare was determined for reassessment (either at a regularly scheduled or unscheduled visit). If the subject does not have absence of GCA signs and symptoms within approximately 4 weeks after the visit in which flare was determined, they will be discontinued from study drug. Subjects who discontinue study drug should receive treatment at the investigator's judgment, in accordance with local standard-of-care (which could include tocilizumab) and continue to follow the regular visit schedule for Period 2 and adhere to the study procedures.

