10.0 Safety Analyses

10.1 General Considerations

Unless otherwise specified, safety data will be summarized on SS1 for Period 1, SS2 for Period 2 and SS LT across Period 1 and Period 2. Safety analysis will include adverse events, laboratory, and vital signs measurements. Safety summaries will be presented by treatment group in each safety analysis set, including a total group for all subjects on active study treatment.

For the safety analysis, subjects are assigned to a treatment group based on the treatment actually received, regardless of the treatment randomized.

Missing safety data will not be imputed.

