10.2.6 Adverse Events of Special Interest

Adverse events of special interest (AESIs) will be summarized by SOC and PT and will be based on standardized or AbbVie-defined company MedDRA queries (SMQs or CMQs), PTs, or based on adjudication results. Adjudicated cardiovascular events will be summarized and presented by treatment group using the CAC adjudicated categories. Adverse events of special interest are categorized as follows:

Upadacitinib
M16-852 – Statistical Analysis Plan
Version 2.0 – 14 February 2024

[figure not shown]
- Serious Infections
- Opportunistic Infection excluding Tuberculosis and Herpes Zoster
- Herpes Zoster
- Active Tuberculosis
- Malignancy
- Non-Melanoma Skin Cancer (NMSC)
- Malignancy excluding NMSC
- Lymphoma
- Adjudicated Gastrointestinal Perforations
- Anemia
- Neutropenia
- Lymphopenia
- Renal Dysfunction
- Hepatic Disorder
- Creatine Phosphokinase (CPK) Elevation
- Adjudicated MACE
- Adjudicated Embolic and thrombotic events (non-cardiac, non-central nervous system [CNS])
 - Adjudicated Venous Thromboembolic Events
 - o Adjudicated Arterial Thromboembolic Events

In addition to AESIs, the following adverse events will also be summarized.

- Bone fracture
- Retinal detachment

Detailed information about the search criteria is provided in Appendix B.

A Forest Plot will be utilized to visualize the overview of all AESIs along with risk differences and 95% CI. A similar Forest Plot will be provided for bone fracture and retinal detachment.

Exposure adjusted event rate (per 100 patient-years) for AESIs as well as bone fracture and retinal detachment will also be summarized on SS1 for Period 1 and SS LT for long term.

Time to the first occurrence of event will also be analyzed using Kaplan-Meier estimates in SS1 and SS LT for each AESI, and displayed as cumulative incidence plots. Similar plots will be provided for the adverse events of bone fracture and retinal detachment.

Tabular listings of AESIs and adverse events of bone fracture and retinal detachment will be provided.

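### For the Period 2 continue-versus-withdraw safety comparison the SAP plans no exposure-adjusted or time-to-event analysis, although time at risk may differ between the arms

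*SAP*

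**What the plan says.** SAP 10.1 sets a default, which applies where a section names no other set: "safety data will be summarized on SS1 for Period 1, SS2 for Period 2 and SS LT across Period 1 and Period 2". Two later sections do specify otherwise.

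- SAP 10.2.4, TEAE rates per 100 patient-years: "Exposure-adjusted TEAEs will be summarized on SS1 for Period 1 and SS LT for long-term". The incidence rate censored at first event is optional: it "may be conducted for selected AESI endpoints as appropriate on SS LT for long-term".
- SAP 10.2.6, AESI event rates: these "will also be summarized on SS1 for Period 1 and SS LT for long term".
- SAP 10.2.6, AESI curves: "Time to the first occurrence of event will also be analyzed using Kaplan-Meier estimates in SS1 and SS LT for each AESI".

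SAP 4.0 defines SS LT by receipt of the same study drug in both periods. Subjects re-randomised from upadacitinib to placebo are therefore outside it.

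Two rules fix how long a Period 2 subject can contribute an event. Under SAP 2.3 (and Protocol 4.1), if GCA signs and symptoms have not cleared "within approximately 4 weeks after the visit in which flare was determined, they will be discontinued from study drug". Under SAP 10.2.1 a TEAE is one that "begins or worsens in severity after initiation of study drug through 30 days post-study drug dosing". Protocol 6.1 ends routine AE collection at the same 30 days. Protocol 5.8 also lets the investigator stop study drug at discretion after a Period 2 flare.

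**The concern.** The Period 2 objective (Protocol 3.1, SAP 2.1) names the safety as well as the efficacy of continuing versus withdrawing upadacitinib. One side of that contrast, the subjects switched to placebo, has no planned exposure-adjusted rate and no planned AESI time-to-event analysis.

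A crude percentage compares arms fairly only if they are observed for similar lengths of time. Here observation ends with study drug, and study drug can end because of a flare, which is the outcome that withdrawal is meant to test. If flares are commoner after withdrawal, the withdrawn arm has less time in which to record an event. Some difference in percentages would then appear with identical event rates. The SAP uses rates for Period 1 and long term, but not in the randomised withdrawal period.

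**Working it through.** **What is planned for Period 2 alone.** SAP 10.2.2 and 10.2.3 give numbers and percentages of subjects, and 10.2.5 and 10.2.6 add listings. The 10.1 default does not restore rates on SS2, because 10.2.4 and 10.2.6 name other sets. SS LT does not supply them either: it omits the switched subjects and pools Period 1 with Period 2 for everyone else. Protocol 7.4 runs the combined-period analysis on the Period 1 safety set, which also yields no Period 2 rate.

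**Size.** The documents give no Period 2 flare, discontinuation or event rates, so there is no plan figure to reproduce. The inputs are:

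- From the documents: 52-week period; stop about 4 weeks after flare; window ends 30 days after last dose; 2:1 re-randomisation.
- Assumed: 50% flare after withdrawal and 20% on continued drug; flare times uniform over 52 weeks; a share *s* of flares ends drug (25%, 50%, 100%); the same constant event hazard in both arms. The only support for the 50% is Protocol 2.1, which reports for a different drug class that "over half of subjects relapsed (as early as 3 months) after discontinuation of IL-6R blockade". The 20% has no source in the documents.

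Full window: W = 52 + 30/7 = 56.29 weeks.

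Mean time lost per flare that ends drug: L = 48²/(2 × 52) = 22.15 weeks.

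Mean window for an arm with flare proportion p: W − p × s × L. For example, at s = 25% the withdrawn arm has 56.29 − 0.50 × 0.25 × 22.15 = 53.5 weeks.

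With one-year risk r, the weekly hazard is λ = −ln(1 − r)/52. A flare that ends drug lowers the chance of a recorded event by

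D = (1/52) × [e^(−λ(4 + 30/7)) × (1 − e^(−48λ))/λ + 4e^(−λW)] − e^(−λW).

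- r = 20%: D = 0.8655 − 0.7854 = 0.080
- r = 80%: D = 0.3854 − 0.1752 = 0.210

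Spurious excess on continued drug: (0.50 − 0.20) × s × D.

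| s | Window, withdrawn | Window, continued | Shorter by | Excess, r = 20% | Excess, r = 80% |
|---|---|---|---|---|---|
| 25% | 53.5 wk | 55.2 wk | 3% | 0.6 points | 1.6 points |
| 50% | 50.7 wk | 54.1 wk | 6% | 1.2 points | 3.2 points |
| 100% | 45.2 wk | 51.9 wk | 13% | 2.4 points | 6.3 points |

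**Second model.** Time to leaving drug is taken as exponential, with 10% leaving on continued drug (assumed) and equal event rates of 5 to 100 first events per 100 patient-years. The ratio of crude percentages, continued to withdrawn, depends on the share leaving after withdrawal:

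- 10% leave: 1.00
- 20% leave: 1.04–1.05
- 30% leave: 1.09–1.12
- 50% leave: 1.22–1.28

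The true rate ratio is 1.00 throughout. At 10 events per 100 patient-years with 30% leaving, the crude figures are 9.8% versus 8.8%.

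**The case against.** The strongest reply is that unequal exposure is assumed. No passage says that withdrawn subjects leave study drug earlier. A Period 2 flare leads first to open-label corticosteroid with study drug continuing, and a subject whose flare clears may stay on it. The row in which every flare ends drug conflicts with that path, so it is only an outer bound. This stands.

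The effect is also small against the noise. If 60% of 210 subjects on 15 mg qualified (the planning remission rate, 40% + 20%, borrowed here), 126 would be re-randomised as 84 and 42. The 95% half-width for a difference at 20% risk is 1.96 × √(0.16 × (1/84 + 1/42)) = 0.148, about 15 points. For an event with 5% one-year risk the spurious excess is only about 0.2–0.3 points, or 0.6 at the bound. This stands too.

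Nor is a formal Period 2 AE contrast specified: the AE differences with confidence intervals in SAP 10.2.2 are for SS1. The distortion would affect a reader's informal comparison, not a stated inference. That limits the weight of the point, but the comparison is the one that the objective invites.

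Finally, a reader might infer that all Period 2 harms are reported only as crude percentages. The documents do not support that. Period 2 events of subjects who keep the same drug enter the SS LT rates and curves, and SAP 6.0 summarises treatment duration on SS2, so unequal exposure would be visible and a rough rate could be derived. No such rate is planned, however.

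**Conclusion.** The gap is real and rests on the SAP's wording: no rate or time-to-event analysis is planned for Period 2 alone, and none at all covers the switched subjects in Period 2. Its likely size is modest. Under the stated assumptions, with 25–50% of flares ending drug, the spurious excess is 0.6–1.2 points at 20% one-year risk and 1.6–3.2 points at 80%. The outer bounds are 2.4 and 6.3 points, and the excess is nil if the arms leave drug equally.

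A reader might go further and conclude that the percentages will overstate the harm of continuing upadacitinib. The documents do not establish this. It follows only if withdrawn subjects do stop earlier and the true hazards are equal. Subjects who flare receive escape corticosteroids, which may change their AE risk, and AE-driven stopping on continued drug could reverse the imbalance. The net direction is uncertain.

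**What to change.** In SAP 10.2.4 and 10.2.6, add SS2 to the named analysis sets for exposure-adjusted TEAE and AESI rates per 100 patient-years and for Kaplan-Meier time to first AESI. Measure time at risk from the first Period 2 dose to the end of the Period 2 TEAE window. Present the results by treatment sequence beside the crude percentages. Show re-randomised subjects separately, because SS2 also holds subjects who continued on their original assignment without re-randomisation.

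State in the text that this corrects for length of observation only, and not for informative stopping or escape corticosteroids.

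The cost is SAP wording and existing table shells run on one more set. No new data are needed, and no confirmatory test or treatment rule changes. The downside is a few more descriptive tables with low precision.

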10.2.6 Adverse Events of Special Interest

Adverse events of special interest (AESIs) will be summarized by SOC and PT and will be based on standardized or AbbVie-defined company MedDRA queries (SMQs or CMQs), PTs, or based on adjudication results. Adjudicated cardiovascular events will be summarized and presented by treatment group using the CAC adjudicated categories. Adverse events of special interest are categorized as follows:

Upadacitinib
M16-852 – Statistical Analysis Plan
Version 2.0 – 14 February 2024

[figure not shown]
- Serious Infections
- Opportunistic Infection excluding Tuberculosis and Herpes Zoster
- Herpes Zoster
- Active Tuberculosis
- Malignancy
- Non-Melanoma Skin Cancer (NMSC)
- Malignancy excluding NMSC
- Lymphoma
- Adjudicated Gastrointestinal Perforations
- Anemia
- Neutropenia
- Lymphopenia
- Renal Dysfunction
- Hepatic Disorder
- Creatine Phosphokinase (CPK) Elevation
- Adjudicated MACE
- Adjudicated Embolic and thrombotic events (non-cardiac, non-central nervous system [CNS])
 - Adjudicated Venous Thromboembolic Events
 - o Adjudicated Arterial Thromboembolic Events

In addition to AESIs, the following adverse events will also be summarized.

- Bone fracture
- Retinal detachment

Detailed information about the search criteria is provided in Appendix B.

A Forest Plot will be utilized to visualize the overview of all AESIs along with risk differences and 95% CI. A similar Forest Plot will be provided for bone fracture and retinal detachment.

Exposure adjusted event rate (per 100 patient-years) for AESIs as well as bone fracture and retinal detachment will also be summarized on SS1 for Period 1 and SS LT for long term.

Time to the first occurrence of event will also be analyzed using Kaplan-Meier estimates in SS1 and SS LT for each AESI, and displayed as cumulative incidence plots. Similar plots will be provided for the adverse events of bone fracture and retinal detachment.

Tabular listings of AESIs and adverse events of bone fracture and retinal detachment will be provided.

10.3 Analysis of Laboratory Data

Selected clinical laboratory tests defined in the protocol operations manual (e.g., hematology, clinical chemistry) will be summarized on SS1 for Period 1 and SS LT for long term.

Baseline is defined as the last non-missing measurements recorded on or before the date of the first dose of study drug. For the analysis of laboratory data, values observed within 30 days of the last dose of study drug will be included.

Each laboratory variable will be summarized for all time points (starting with Baseline) with the number of non-missing observations, mean and standard deviation, median, minimum and maximum. Mean change from Baseline to each applicable post-baseline visit will be summarized for selected laboratory variables, with the number of observations, Baseline mean, and visit mean. In Period 1, mean change from Baseline will be compared between treatment groups using a one-way Analysis of Variance (ANOVA), with treatment as a fixed factor. The change from Baseline mean, standard error, and 95% confidence interval will be presented for the mean change from Baseline within each treatment group and difference between treatment groups.

[figure not shown]
Laboratory abnormalities will be evaluated based on Potentially Clinically Important (PCI) criteria (Appendix C). For each laboratory PCI criterion, the number and percentage

of subjects who have a laboratory value meeting the criteria will be summarized. Listings will be provided to summarize subject-level laboratory data for subjects meeting PCI criteria.

Changes in laboratory parameters will be tabulated using shift tables by National Cancer Institute (NCI) Common Terminology Criteria (CTC) (version 4.03). Selected lipid parameters will be summarized using National Cholesterol Education Program (NCEP) Adult Treatment Panel III (ATPIII) guidelines (Appendix D). A shift table from Baseline to the worse value during treatment will be created. A similar shift table will be provided to summarize shifts from Baseline to the final post-baseline value.

In addition, ALT/SGPT, AST/SGOT, alkaline phosphatase, and total bilirubin will be categorized as follows:

- ALT $> 3 \times ULN$
- ALT $> 5 \times ULN$
- $ALT > 10 \times ULN$
- $ALT > 20 \times ULN$
- $AST > 3 \times ULN$
- $AST > 5 \times ULN$
- AST $> 10 \times ULN$
- $AST > 20 \times ULN$
- $TBL > 2 \times ULN$
- Alkaline phosphatase (ALP) $> 1.5 \times ULN$
- ALT and/or AST $> 3 \times ULN$ and TBL $> 1.5 \times ULN$
- ALT and/or AST $> 3 \times ULN$ and TBL $> 2 \times ULN$
- ALT and/or AST > 3 × ULN and TBL > 2 × ULN and alkaline phosphatase $< 2 \times ULN$

A listing of ALT, AST, total bilirubin (and direct and indirect bilirubin, if available), and alkaline phosphatase values for subjects meeting the laboratory criteria specified above will be provided.

In addition, eDISH plots will be created displaying post-baseline total bilirubin versus post-baseline ALT, in terms of the maximum ratio relative to the ULN (not necessarily concurrent) for both SS1 and SS LT.

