7.4 Statistical Analyses for Safety

Safety analyses for Period 1 and Period 2 alone and long-term safety analyses for Period 1 and Period 2 combined will be carried out using the Safety Analysis Set in Period 1 (for safety analyses for Period 1 alone and Periods 1 and 2 combined) as well as the Safety Analysis Set in Period 2 (for safety analyses for Period 2 alone) respectively, and will be based on treatments actually received regardless of the randomly assigned treatment.

Safety will be assessed by treatment-emergent adverse events (TEAEs), physical examination, laboratory assessments, ECG, and vital sign results. The number and percentage of subjects experiencing TEAEs by treatment group will be tabulated by the Medical Dictionary for Regulatory Activities (MedDRA) system organ class (SOC) and preferred term (PT). In addition, summaries of SAEs and TEAEs by severity and relationship to study drug as assessed by the investigator will be provided. SAEs, severe TEAEs, and TEAEs that lead to premature study discontinuation will be listed. Changes in vital signs, physical examination results, and clinical laboratory variables at each visit as compared to baseline will be summarized. Shift of laboratory values from baseline to defined time points will be tabulated.

Missing safety data will not be imputed.

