- The estimand corresponding to the multiplicity-controlled secondary endpoint of time to first disease flare is defined as the difference in the time to first disease flare in either upadacitinib 15 mg QD or 7.5 mg QD in combination with a 26-week CS taper regimen group and placebo in combination with a 52-week CS taper regimen group in subjects with GCA, regardless of premature discontinuation from study drug, or receiving more than 100 mg prednisone (or equivalent) systemic CS for a non-GCA indication.
- The estimand corresponding to the multiplicity-controlled secondary endpoint of number of disease flare per subject is defined as the difference in the

exposure-adjusted number of disease flare per subject between either upadacitinib 15 mg QD or 7.5 mg QD in combination with a 26-week CS taper regimen group and placebo in combination with a 52-week CS taper regimen group in subjects with GCA, regardless of premature discontinuation from study drug, or receiving more than 100 mg prednisone (or equivalent) systemic CS for a non-GCA indication.

The objective of Period 2 is to evaluate the safety and efficacy of continuing versus withdrawing upadacitinib in maintaining remission in subjects who achieved remission in Period 1.

[figure not shown]

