4.0 Analysis Populations

The following population sets will be used for the analyses.

- The Full Analysis Set (FAS) will be defined for Period 1 and Period 2.
 - The FAS in Period 1 (FAS1) consists of all randomized subjects who received at least 1 dose of study drug in Period 1.
 - The FAS in Period 2 (FAS2) consists of all subjects who achieved remission for at least 24 consecutive weeks prior to the Week 52 Visit (at the end of Period 1) and received at least 1 dose of study drug in Period 2.
- An exploratory analysis set (FAS2 E) is defined for Period 2 to include all subjects who had absence of GCA signs and symptoms AND were CS-free at the Week 52 visit, but did not achieve remission for at least 24 consecutive weeks prior to the Week 52 Visit, and continued and received at least 1 dose of study drug in Period 2 on their originally randomized treatment assignment.
- The Per-Protocol Analysis Set is defined to represent a subset of the FAS1 subjects without any major protocol violations during the study which are expected to impact the primary endpoint. The final criteria and the exclusion of subjects for the Per-Protocol Analysis Set will be finalized before the database lock for Primary Analysis. The Per-Protocol Analysis Set will be used to analyze the primary efficacy endpoint as a supplementary analysis.
- The Safety Analysis Set in Period 1 (SS1) consists of all subjects who received at least 1 dose of study drug in Period 1.
- The Safety Analysis Set in Period 2 (SS2) consists of all subjects who received at least 1 dose of study drug in Period 2.
- The Long-Term Safety Analysis Set (SS LT) consists of all subjects who received at least one dose of study drug in Period 1 and received the same study drug in Period 2.

Primary efficacy analysis for primary and multiplicity-controlled secondary endpoints will be carried out on FAS1 and SS1 (for the endpoint of rate of CS-related AEs) in Period 1. Efficacy analysis for additional endpoints in Period 1 will be carried out on FAS1, and efficacy analysis for additional endpoints in Period 2 will be carried out on FAS2.

Exploratory efficacy analyses for Period 2 will be conducted for additional endpoints in Period 2 on FAS2 E. For all efficacy analyses, subjects will be grouped according to treatment (or treatment sequence) as randomized.

For Safety Analysis Sets, subjects are assigned to a treatment group based on the treatment actually received, regardless of the treatment randomized.

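### SAP 10.3 names no analysis set containing the Period 2 laboratory values of subjects re-randomised from upadacitinib to placebo, so the laboratory side of continue versus withdraw has no clearly planned summary

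*SAP*

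**What the plan says.** SAP 10.1 sets a default that applies unless a later section says otherwise: "safety data will be summarized on SS1 for Period 1, SS2 for Period 2 and SS LT across Period 1 and Period 2".

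SAP 10.3 does say otherwise. Selected laboratory tests "will be summarized on SS1 for Period 1 and SS LT for long term". The eDISH plots repeat the same pair: "not necessarily concurrent) for both SS1 and SS LT". The one-way ANOVA of mean change is confined to Period 1, and baseline is defined only relative to the first dose of study drug. The tables of potentially clinically important (PCI) values, the CTC and lipid shift tables, and the liver-category counts name no set of their own.

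SAP 4.0 defines SS LT as the set that "consists of all subjects who received at least one dose of study drug in Period 1 and received the same study drug in Period 2". By contrast, "The Safety Analysis Set in Period 2 (SS2) consists of all subjects who received at least 1 dose of study drug in Period 2".

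Protocol 7.4 states: "Safety analyses for Period 1 and Period 2 alone and long-term safety analyses for Period 1 and Period 2 combined will be carried out". It assigns the Period 2 analyses to the Period 2 safety set and counts laboratory variables as part of safety. SAP 2.1 gives the Period 2 objective as "to evaluate the safety and efficacy of continuing versus withdrawing upadacitinib in maintaining remission".

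**The concern.** Upadacitinib subjects who qualify at Week 52 are re-randomised 2:1 to stay on drug or move to placebo. Those moved to placebo are in SS1, but that set is used for Period 1. They are not in SS LT, because their drug changed. SS2 would hold their Period 2 values, and SAP 10.3 leaves it out without giving a reason.

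Protocol 2.2 lists changes in transaminases, lipids, CPK, hemoglobin and white cells as observed with upadacitinib. In Period 1, upadacitinib with a 26-week taper is compared with placebo with a 52-week taper, so a laboratory difference there mixes drug with scheduled steroid. Continue versus withdraw is the only randomised upadacitinib-versus-placebo laboratory comparison in which the two arms do not have different scheduled tapers. It is also where reversal after stopping would be seen. With baseline fixed before the first Period 1 dose, reversal has no planned reference value either.

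**Working it through.** **1. Which named set holds which Period 2 laboratory values**

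| Period 2 path | SS1 (used for Period 1) | SS LT | SS2 |
|---|---|---|---|
| Upadacitinib, then same dose | no | yes | yes |
| Placebo, then placebo | no | yes | yes |
| Upadacitinib, then placebo | no | **no** | yes |

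Only the third row depends on SS2. The omission looks specific to laboratory data: SAP 10.4 on vital signs names no set and so keeps the SAP 10.1 default, SS2 included.

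**2. The planning rate used for size**

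SAP 2.4 assumes 40% on placebo and a 20-point difference, so 60% at 15 mg, and states at least 90% power with Fisher's exact test at two-sided 0.05. Exact enumeration with 210 versus 105 subjects gives power 0.910, so the stated figure reproduces. The 60% is a rate of sustained remission from Week 12 to Week 52. The re-randomisation criterion is different (24 consecutive weeks before Week 52, on the taper or steroid-free), so using 60% for it is an assumption. No rate is given for 7.5 mg; 40–60% is assumed.

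**3. Subjects withdrawn** = arm size × rate × 1/3

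- 15 mg, planned: 210 × 0.60 = 126 re-randomised; 126/3 = 42 withdrawn, 84 continued.
- 7.5 mg, planned: 105 × 0.40 to 0.60 = 42 to 63 re-randomised; one third is 14 to 21 withdrawn.
- Total: 42 + 14 = 56 to 42 + 21 = 63.
- With the 428 enrolled (SAP 9.1) at 2:1:1, that is 214 and 107: 42.8 + 14.3 = 57.1 to 42.8 + 21.4 = 64.2.
- With a common rate of 40–80% in both upadacitinib arms: 321 × 0.40/3 = 42.8 to 321 × 0.80/3 = 85.6, about 43 to 86.

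**4. Panels**

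Protocol Appendix D schedules hematology and chemistry at Weeks 56, 60, 80, 92 and 104, which is five visits. The ceiling is 56 × 5 = 280 to 63 × 5 = 315. It is reached only if everyone attends every visit on drug: SAP 10.3 keeps values only within 30 days of the last dose, and a subject whose flare is unresolved at about 4 weeks stops study drug. Lipids are scheduled once in Period 2, at Week 80.

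**5. Precision of continue versus withdraw**

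95% half-width in SD units = 1.96 × √(1/n withdrawn + 1/n continued), with equal SDs and complete values:

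- 15 mg, 42 versus 84: 1.96 × √(1/42 + 1/84) = 0.37.
- 7.5 mg, 14 versus 28: 1.96 × √(1/14 + 1/28) = 0.64.
- 7.5 mg, 21 versus 42: 1.96 × √(1/21 + 1/42) = 0.52.

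**The case against.** The strongest reply is that the gap is narrower than it first appears. Much of that stands.

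- A reader might infer that these subjects' laboratory data are never analysed. The documents do not support that. The PCI, shift and liver-category outputs name no set, so the SAP 10.1 default could bring in SS2; equally, the opening sentence of SAP 10.3 could govern them. The text does not settle it. Anemia, neutropenia, lymphopenia, hepatic disorder and CPK elevation are adverse events of special interest, and their basic summaries fall under the SS2 default. This cover is partial, since it depends on events being reported, and the exposure-adjusted rates and cumulative incidence plots in SAP 10.2.6 are again on SS1 and SS LT. ESR and hsCRP enter complete remission at Week 104 on FAS2.
- A reader might infer that this is the only laboratory comparison free of unequal tapers. It is not: 15 mg and 7.5 mg share the 26-week taper, and the Period 1 ANOVA compares treatment groups.
- A reader might infer that re-randomised subjects all followed the same taper to zero and that Period 2 is steroid-free. Neither holds. A steroid-free subject who earlier had escape therapy can qualify (Protocol 4.1 and 5.8), and Period 2 flares bring open-label steroids, possibly more often in one arm.
- Protocol 7.4 promises summaries and shifts from baseline. It does not promise a continue-minus-withdraw difference or a Period 2 baseline, so those parts of the fix are recommendations drawn from the Period 2 objective. Adding SS2 is what consistency with the protocol requires.

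**Conclusion.** The point holds in a limited form. For the summaries and eDISH plots whose sets are stated, SAP 10.3 leaves out the Period 2 laboratory values of subjects moved from upadacitinib to placebo, contrary to the SAP 10.1 default and Protocol 7.4. For the remaining laboratory tables the set is ambiguous.

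The number affected is about 56–63 subjects on the planned sample, given the assumed rates, and about 43–86 over the wider range with 428 enrolled. The panel count is an upper bound. The comparison at stake is randomised and has no difference in scheduled taper between its arms, but it is not free of steroid imbalance, and its precision is modest: about ±0.37 SD at 15 mg and wider at 7.5 mg. No primary or multiplicity-controlled result is touched. The documents do not show the current status of Period 2, so nothing here rests on whether it is still running.

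**What to change.** In SAP 10.3:

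- Add SS2 for Period 2 and state that it applies to the summaries, PCI counts, shift tables, liver categories and eDISH plots.
- Present SS2 by treatment sequence. Naming SS2 alone could pool subjects withdrawn from upadacitinib with those on placebo throughout. SAP 9.5 already uses the continue and withdraw sequences for efficacy.
- Define a Period 2 baseline as the last value before the first Period 2 dose. For lipids, Appendix D shows no Week 52 test, so the last scheduled value is from Week 24; say so in the table.
- Among re-randomised subjects, give continue-minus-withdraw differences with 95% CIs within each dose, labelled descriptive, and note that flare steroids may differ by arm.

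If the omission is intended, state the reason and reconcile it with Protocol 7.4. The cost is SAP wording and one extra set of tables from data already scheduled for collection; no visit, sample or trial procedure changes.
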